3.3.2 Visit 2 - Baseline (Day 0)

If screening and baseline are conducted on the same day, all duplicate steps need only be completed once.

- 3.3.2.1 Record and check: any AEs and SAEs, concomitant medications since the last visit[X4] (Record all concomitant medications, with particular attention to systemic corticosteroids, calcium hydroxybenzoate, and whether hypoglycemic medications were used during the period)
- 3.3.2.2 Further review of inclusion/exclusion criteria
- 3.3.2.3 Randomize patients into groups. Divide into Group A (intervention group) and Group B (control group).
 - 3.3.2.4 Develop a diabetes treatment plan for patients according to the "Chinese Guidelines for the Prevention and Treatment of Type 2 Diabetes (2020 Edition)" [13]. Due to the risk of hypoglycemia, sulfonylureas, glinides, insulin, and insulin analogues are prohibited in this study.
- 3.3.2.5 Hypoglycemia: Investigators should instruct participants to complete a participant diary and monitor blood glucose levels as frequently as possible using a blood glucose meter when hypoglycemia occurs. If

hypoglycemic symptoms do not improve after carbohydrate supplementation, participants should seek medical attention at a hospital. If hypoglycemic symptoms are suspected, investigators should diagnose the condition and record it in the CRF. Investigators should classify events according to the following categories:

- 1) Severe hypoglycemia: An event requiring assistance from another person to administer carbohydrates, glucagon, or other resuscitation measures.
- 2) Documented symptomatic hypoglycemia: During the event, typical symptoms of hypoglycemia are present with measured blood glucose levels ≤70 mg/dL (3.9 mmol/L).
- 3) Asymptomatic hypoglycemia: An event without typical symptoms of hypoglycemia, but with a measured blood glucose concentration ≤70 mg/dL (3.9 mmol/L).
- 4) Possible symptomatic hypoglycemia: During the event, hypoglycemia symptoms were present without blood glucose measurement, but it is suspected that they may have been caused by a blood glucose concentration ≤70 mg/dL (3.9 mmol/L).
- 5) Relative hypoglycemia: Following the event, the diabetic patient reports any typical symptoms of hypoglycemia and symptoms consistent with hypoglycemia, but measured blood glucose concentration is > 70 mg/dL (3.9 mmol/L).

Researchers will collect the following items and record them in the CRF: Symptoms of hypoglycemia; duration (start and end date and time); severity grading (Grade 1 hypoglycemia: blood glucose < 3.9 mmol/L and ≥ 3.0 mmol/L; Grade 2 hypoglycemia: blood glucose < 3.0 mmol/L; Grade 3 hypoglycemia: severe event requiring assistance from others for treatment, accompanied by altered consciousness and/or physical changes, but without specific blood glucose thresholds); Measures taken (self-feeding, assistance required to eat, assistance required to go to the hospital for intravenous glucose infusion; other); Outcome; Blood glucose level measured by a blood glucose meter (at the time of hypoglycemia); Time of blood glucose measurement by a blood glucose meter (at the time of hypoglycemia);

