3.3.6 Visit 5 - Follow-up period (baseline: 84 ± 3 days)

- 3.3.6.1 Physical examination (measurements: weight, waist circumference, blood pressure, pulse rate);
- 3.3.6.2 Collect samples and perform relevant tests: fasting blood glucose, HbA1c, fasting C-peptide, fasting insulin, glycated albumin (GA); Complete blood count: red blood cells (RBC), white blood cells (WBC), platelets (PLT), hemoglobin (HGB);Liver and kidney function: total bilirubin (Tbil), alanine transaminase (ALT), aspartate transaminase (AST), total protein (TP), albumin, blood urea nitrogen (BUN) or urea (Urea), serum creatinine (Cr), uric acid (UA);Lipid profile: Total cholesterol (TC), triglycerides (TG), low-density lipoprotein (LDL-C), high-density lipoprotein (HDL-C);
- 3.3.6.3 Determine that the subject has completed the entire trial.
- 3.3.7 Each center measures GA frozen samples.

3.4 outcome measures

3.4.1 Primary endpoint:

Proportion of participants achieving HbA1c < 7% at Visit 5 (Week 12 \pm 3 days from baseline).

3.4.2 Secondary endpoints:

- 3.4.2.1 Proportion of participants achieving HbA1c < 6.5% at Visit 5.
- 3.4.2.2 Change in HbA1c levels from baseline to Visit 5.
- 3.4.2.3 Incidence and frequency of hypoglycemia
- 3.4.2.4 Changes in pancreatic β -cell function (HOMA- β = 20 × FINS / (FPG 3.5));
- 3.4.2.5 Changes in insulin resistance levels (HOMA-IR = FINS \times FPG/22.5);
- 3.4.2.6 Changes in body weight, waist circumference, and BMI;

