7.4.2 Secondary Endpoint Analysis

Analysis will be conducted using both FAS and PPS.

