*** Hypoglycemia Incidence and Frequency:**

Calculate the number of episodes, total number of episodes, and percentage of participants in the intervention group and control group who experienced hypoglycemia during each visit (V3A—control group visit/V3B—intervention group visit, V4). For hypoglycemia incidence rates, use chi-square tests or Fisher's exact probability test for between-group comparisons.

List the hypoglycemia episodes experienced by participants at each visit.

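### The hypoglycemia analysis in SAP 7.4.2 stops at Visit 4, compares arms on the FAS and PPS rather than the Safety Set, and does not separate events with a low reading from those without one

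*Protocol*

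**What the plan says.** Protocol 3.4.2 and SAP 4.1.2 name the secondary endpoint only as "Incidence and frequency of hypoglycemia". SAP 4.1.2 places it among the efficacy endpoints and states that secondary endpoints are evaluated to the end of treatment at Visit 5.

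SAP 7.4.2 gives the analysis. Episodes and affected participants are tabulated by visit, and the visits listed are 3A for control, 3B for intervention, and 4. On testing it says: "For hypoglycemia incidence rates, use chi-square tests or Fisher's exact probability test for between-group comparisons". For all secondary endpoints the set is given as "Analysis will be conducted using both FAS and PPS". Protocol 5.1 assigns efficacy to the FAS and PPS and safety to the Safety Set.

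Protocol 3.3.2.5 defines five event classes. Class 1 is "Severe hypoglycemia: An event requiring assistance from another person to administer carbohydrates, glucagon, or other resuscitation measures". Class 2 is an event in which "typical symptoms of hypoglycemia are present with measured blood glucose levels ≤70 mg/dL (3.9 mmol/L". Class 3 has the same glucose limit without symptoms. Class 4 has symptoms but no measurement. Class 5 has symptoms, "but measured blood glucose concentration is > 70 mg/dL (3.9 mmol/L". A separate severity grading for the CRF starts with "Grade 1 hypoglycemia: blood glucose < 3.9 mmol/L and ≥ 3.0 mmol/L".

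**The concern.** Hypoglycemia is the only harm outcome for which the SAP names a between-group test. The other adverse event tables are descriptive. Three features of its specification matter.

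- **Window.** The visit list ends at week 8, so the last four weeks of treatment are not counted. The arms diverge by design only from the week-4 visit, so the lost weeks are a large part of the period in which GA-guided adjustment could cause harm.
- **Analysis set.** A harm outcome is compared on efficacy sets, one of which is selected on compliance after randomisation.
- **Event definition.** Nothing says which classes count. The protocol prohibits the drug classes it associates with hypoglycemia and calls the remaining risk extremely low. A few symptom reports with no low reading could therefore decide the comparison, in a trial where no blinding is described and Group A patients are told their GA result.

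**Working it through.** **1. Window.** Inputs from Table 1 (both documents): Visit 3A on day 28 ± 3, Visit 3B up to 5 days later, Visit 4 on day 56 ± 3, Visit 5 on day 84 ± 3.

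- Uncounted time: 84 − 56 = 28 days.
- Share of follow-up: 28/84 = 33%. At the extremes of the visit windows: (81 − 59)/81 = 22/81 = 27%, and (87 − 53)/87 = 34/87 = 39%.
- Share of the time after the GA adjustment: 28/(84 − 28) = 28/56 = 50% if Visit 3B is on day 28, and 28/(84 − 33) = 28/51 = 55% if it is on day 33.
- Share of the counted time that follows the adjustment: (56 − 28)/56 = 50% under the SAP list, against (84 − 28)/84 = 67% if counting runs to Visit 5.

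If episodes arise at a constant rate and everyone is followed to Visit 5 (both assumptions), a third of expected episodes go uncounted. The documents give no event rate, so the loss cannot be stated as a number of patients.

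**2. Are the data collected?** Table 1 has diaries handed out at Visit 4, participants' reports checked and collected at Visit 5, and (S)AEs since the previous visit reviewed at Visit 5. The information for weeks 8 to 12 should therefore be available.

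**3. Analysis sets.**

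| Set | Entry rule | Effect on a harm comparison |
|---|---|---|
| FAS | Randomised, eligible, baseline HbA1c present | Keeps non-compliant patients |
| PPS | FAS plus good compliance and no important deviation; criteria settled at data verification | Can remove patients who miss doses, including after an event |
| Safety Set | At least one safety assessment | Not selected on compliance |

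**4. Classes against grades.**

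| Event | Class | Glucose-based grade |
|---|---|---|
| Reading 3.8 | 2 or 3 | Grade 1 |
| Reading 3.9 | 2 or 3 | none |
| Reading 4.0 with symptoms | 5 | none |
| Symptoms, no reading | 4 | none |

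SAP 7.4.2 counts all of these rows alike, because it neither includes nor excludes any class. The units are not the problem: 70/18.016 = 3.885 mmol/L (standard conversion factor, assumed), which rounds to 3.9. The conflict is between ≤ and <. The severe definitions also differ: class 1 needs assistance only, while Grade 3 adds altered consciousness and/or physical changes.

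**5. Frequency.** Episode totals are tabulated, but no follow-up time is attached to them. Follow-up will vary: pilot completion was 72.5%, and SAP 7.2.1 imputes nothing. The first interval can also be up to 5 days longer in Group A (5/28 = 18%), so first-visit counts are not strictly like for like.

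**The case against.** **The visit list may be a slip.** SAP 4.1.2 runs secondary endpoints to Visit 5, so a programmer might include that visit anyway. On the other side, the narrative for Visit 5 in Protocol 3.3.6, unlike that for Visit 4, does not list recording of hypoglycemia, which could explain the shorter list. Either way the documents disagree, and the analysis section read literally excludes Visit 5. The point stands.

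**The Safety Set is not bypassed.** Protocol 3.3.4.3 treats hypoglycemia as an adverse event, and SAP 7.5.2 with Protocol 5.7 summarises adverse events by group on the Safety Set. This is correct. What remains is that the tested comparison is made elsewhere. The FAS keeps non-compliant patients and may differ little from the Safety Set, so the PPS is the main worry. An investigator's dose reduction for unexplained hypoglycemia is permitted, and adherence is measured against the prescribed dose, so that alone would not be non-compliance. Only unprescribed stopping or missed doses would matter.

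**A rare secondary outcome may reasonably be described without a model.** This is accepted. With few events a Poisson or negative binomial fit may be unstable, and the lack of one is not a defect.

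**Unseen text may settle some of this.** SAP 7.2.3 (Special Data Notes) is in the contents list but not in the text available, the table shells are separate, and the SAP cites Protocol 3.0 while the protocol supplied is 2.0.

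Two stronger readings are not supported. A reader might infer that the 3.9 boundary conflict distorts the tested result. It does not: no visible SAP analysis uses the grades, and a reading of 3.9 is still an event. A reader might also infer that Group A's additional visit gives it more chances to report events. In Table 1, event review at Visit 3A is for Group B only and at Visit 3B for Group A only, so each arm has three scheduled follow-up reviews: 3A or 3B, then 4, then 5.

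**Conclusion.** The point holds for the window, the analysis set and the event definition. As written, the tested hypoglycemia comparison omits 28 of 84 days (27% to 39% across the visit windows) and 50% to 55% of the time after the GA adjustment. Both arms lose the same period, so the omission need not favour one arm. It does under-report harm, and it weights the comparison toward weeks in which the arms were managed alike. The effects of the PPS and of mixing classes cannot be sized, because the documents give neither event rates nor the final PPS criteria.

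The primary endpoint is unaffected. The conclusion rests on the visible text of SAP 7.4.2 and Table 1 and would change if a counting rule in text not seen here already extends to Visit 5. The ≤3.9 versus <3.9 mismatch is a separate, minor inconsistency confined to readings of exactly 3.9 mmol/L.

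**What to change.** In SAP 7.4.2:

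1. Count all hypoglycemic events from randomisation to Visit 5 in both arms, keeping any by-visit table as a supplement that includes Visit 5.
2. Make the Safety Set the main set for the between-group comparison. FAS and PPS results can be supportive.
3. Present severe plus glucose-documented events (classes 1 to 3) separately from classes 4 and 5, and say in advance which is compared.
4. Report episodes per person-time by arm alongside incidence. A rate model is optional, given how few events are expected.

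Separately, reconcile the class and grade definitions in Protocol 3.3.2.5, both at the 3.9 mmol/L boundary and for severe events. Which clinical threshold is right is not judged here. Align the Visit 5 narrative in Protocol 3.3.6 with Table 1.

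The cost is SAP wording and table shells, using events, dates and glucose values that the CRF is already meant to hold. The one downside is that the main count will contain fewer events once classes 4 and 5 are shown apart. The change should be made before the analysis is run.

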3.3.3 Visit 3A - Follow-up Period (Baseline \pm 3 days)

3.3.3.1 Patients in Group B undergo a physical examination (measurements: weight, waist circumference, blood pressure, pulse rate); blood samples are collected and frozen for storage (to be used for GA measurement at the end of the study); all data are recorded (medication changes, occurrence of hypoglycemia, other safety events). The study physician determines whether patients require medication adjustments based on clinical

guidelines (refer to Figure 2).

3.3.3.2 Patients in Group A undergo blood collection and GA measurement.

3.3.4 Visit 3B - Follow-up Period (Visit 3A + 5 days)

- *Preferably within 3 days after Visit 3A, with a maximum of 5 days.
 - 3.3.4.1 Patients in Group B will not participate in this follow-up visit.
 - 3.3.4.2 Patients in Group A will undergo a physical examination (measurements: weight, waist circumference, blood pressure, pulse rate). The GA results for Group A patients will be communicated to the study physician and the patients. The study physician will adjust the medication based on the GA results.

Drug adjustments follow the "GA normalization" principle: if GA > 16%, the study physician increases the type of oral medication based on the 2020 Chinese Diabetes Prevention and Control Guidelines (Figure 2). Due to the risk of hypoglycemia, sulfonylureas, glinides, insulin, or insulin analogues are prohibited in this study. If $GA \le 16\%$, no drug adjustments are made. However, if a patient reports hypoglycemia within the past month, the cause of hypoglycemia must be identified first and appropriate management provided. Since this study excludes sulfonylureas, glinides, insulin, or insulin analogues, the theoretical risk of hypoglycemia is extremely low. If unexplained hypoglycemia occurs, the investigator may consider reducing the dose of oral hypoglycemic agents as appropriate.

3.3.4.3 Record all data (medication status, occurrence of hypoglycemia, and other adverse events).

3.3.5 Visit 4 – Follow-up period (baseline ± 3 days)

- 3.3.5.1 Physical examination (measurements: weight, waist circumference, blood pressure, pulse rate);
- 3.3.5.2 Blood samples collected and frozen for storage in both Group A and Group B (to be measured for GA at the end of the study);
- 3.3.5.3 Record all data (medication changes, occurrence of hypoglycemia, other safety events).
- 3.3.5.4 The study physician conducting this visit should generally not adjust medications. However, adjustments may be made if the patient reports adverse events related to medication. Since this study excludes sulfonylureas, glinides, insulin, and insulin analogues, the theoretical risk of hypoglycemia is extremely low. If the patient reports hypoglycemia within the past month, the cause must first be identified and appropriate management provided. If unexplained hypoglycemia occurs, the investigator may consider reducing the dose of oral hypoglycemic agents as appropriate.

3.3.6 Visit 5 - Follow-up period (baseline: 84 ± 3 days)

- 3.3.6.1 Physical examination (measurements: weight, waist circumference, blood pressure, pulse rate);
- 3.3.6.2 Collect samples and perform relevant tests: fasting blood glucose, HbA1c, fasting C-peptide, fasting insulin, glycated albumin (GA); Complete blood count: red blood cells (RBC), white blood cells (WBC), platelets (PLT), hemoglobin (HGB);Liver and kidney function: total bilirubin (Tbil), alanine transaminase (ALT), aspartate transaminase (AST), total protein (TP), albumin, blood urea nitrogen (BUN) or urea (Urea), serum creatinine (Cr), uric acid (UA);Lipid profile: Total cholesterol (TC), triglycerides (TG), low-density lipoprotein (LDL-C), high-density lipoprotein (HDL-C);
- 3.3.6.3 Determine that the subject has completed the entire trial.
- 3.3.7 Each center measures GA frozen samples.

3.4 outcome measures

3.4.1 Primary endpoint:

Proportion of participants achieving HbA1c < 7% at Visit 5 (Week 12 \pm 3 days from baseline).

3.4.2 Secondary endpoints:

- 3.4.2.1 Proportion of participants achieving HbA1c < 6.5% at Visit 5.
- 3.4.2.2 Change in HbA1c levels from baseline to Visit 5.
- 3.4.2.3 Incidence and frequency of hypoglycemia
- 3.4.2.4 Changes in pancreatic β -cell function (HOMA- β = 20 × FINS / (FPG 3.5));
- 3.4.2.5 Changes in insulin resistance levels (HOMA-IR = FINS \times FPG/22.5);
- 3.4.2.6 Changes in body weight, waist circumference, and BMI;

3.5 Sample size

100 cases each in the intervention group and the control group. Sample size calculation method:

In our previous single-center pilot study (n=40) targeting this research, the results showed that patients whose treatment regimens were adjusted based on GA achieved an HbA1c target rate (<7%) of 76.9% at 3-month follow-up, compared with 46.2% in the control group (p=0.226). Statistical significance was set at P < 0.05, with a statistical power of 0.8 and a 30% difference between the experimental and control groups as the calculation basis. Considering the follow-up completion rate of the pre-experimental patients (72.5%) and other factors such as a multi-center study, the target sample size for this study was determined to be 100 cases each for the intervention and control groups.

3.6 Expected overall duration of the clinical trial

Considering the time required for clinical trial sites to complete all subject enrollment, follow-up, and sample testing, it is estimated that the study will take 18 months from the first subject enrollment to database lock. If the implementation time exceeds the expected duration, the protocol will not be amended.

4. Preliminary Research Basis

In recent years, glycated albumin (GA) has gained increasing attention as an important biological marker for diabetes. The measurement of GA is not affected by albumin concentration, blood glucose levels, bilirubin levels, or lactose. Long-term frozen samples (e.g., the DCCT study, with samples frozen for up to 23 years) remain unaffected by these factors. Additionally, the clinical reference range for GA has been established [7-10]. In the latest edition of the "Chinese Clinical Application Guidelines for Blood Glucose Monitoring (2015 Edition)," glycated albumin (GA) is also proposed as a sensitive indicator of blood glucose changes [12]. Recently, a short-term study conducted by our laboratory found that changes in GA could predict changes in HbA1c levels three months later in newly diagnosed type 2 diabetes patients and type 2 diabetes patients undergoing treatment adjustments. This is the first study to report that GA can predict drug efficacy [8]. Additionally, in a preliminary small-scale pilot study conducted by our team for this research, patients whose treatment regimens were adjusted based on GA achieved an HbA1c target rate (<7%) of 76.9% after three months of follow-up, compared to 46.2% in the control group; Similarly, in the GA-adjusted treatment group, the HbA1c achievement rate (<6.5%) was 30.8%, while the control group was 23.1%.

5. Statistical Analysis

5.1 Analysis Population:

Randomized Population: All subjects who were randomly assigned to a treatment group constitute the randomized population.

Full Analysis Set (FAS): Subjects who were randomly assigned, met the study inclusion criteria, and had baseline measurements for the primary efficacy endpoint. The FAS analysis follows the intention-to-treat (ITT) principle.

Per-Protocol Set (PPS): Participants in the FAS who demonstrated good compliance and had no important protocol deviations that affected the primary efficacy assessment (specific criteria will be confirmed during data verification). Safety Set (SS): All participants with at least one safety assessment are included in the safety analysis.

Efficacy analysis is based on the FAS and PPS, while safety analysis is based on the SS.

5.2 Statistical software used in this study:

Statistical analysis was performed using SAS version 9.4 or higher.

5.3 Baseline and Demographic Characteristics

Demographic data and other baseline characteristics between treatment groups will be described according to group. Quantitative indicators will be statistically described based on data distribution characteristics, including mean, standard deviation, median, quartiles, minimum value, and maximum value. Count data will be statistically described using various frequencies and composition ratios.

5.4 Adherence Analysis

Statistical descriptions of medication adherence records for each visit during the entire treatment period will be provided.

5.5 Analysis of Primary Endpoint Measures

- Proportion of participants with HbA1c < 7% at Visit 5 (Week 12 \pm 3 days).
- The number and percentage of participants achieving HbA1c < 7% and the 95% confidence interval (CI) will be calculated.
- The difference in proportions between groups (intervention control) and its 95% CI will be computed.
- Chi-square test or Fisher's exact test will be used for between-group comparisons.
- Sensitivity analysis: The Cochran-Mantel-Haenszel (CMH) test will be used to adjust for center effects.

5.6 Analysis of Secondary Endpoints

Secondary endpoints includes:

- Proportion with HbA1c \leq 6.5% at Visit 5
- Change in HbA1c from baseline
- Incidence and frequency of hypoglycemia
- Change in $\beta\text{-cell}$ function (HOMA- β = 20 \times FINS / (FPG 3.5))
- Change in insulin resistance (HOMA-IR = FINS \times FPG / 22.5)
- Changes in weight, waist circumference, and BMI
- Categorical variables: Chi-square or Fisher's exact test
- Continuous variables: t-test or Wilcoxon rank-sum test

5.7 Safety analysis

Safety analysis was conducted using the safety analysis set (SS) as the primary analysis set. Adverse events (AEs) and serious adverse events (SAEs) occurring during treatment were summarized and analyzed by treatment group based on

their incidence rates and severity, and classified according to major system organs and medical terminology. Other safety data, including laboratory test results, were analyzed and compared with the screening period using descriptive methods.

6. Case allocation among study centers

This trial uses a competitive enrollment method, and the case allocation plan for each study center is each center will recruit 10 subjects in the control group and 10 subjects in the intervention group, for a total of 100 subjects in the control group and 100 subjects in the intervention group.

7. Subject Protection (if applicable)

This clinical trial will be conducted in accordance with the Declaration of Helsinki (2008 revised edition) and relevant Chinese laws and regulations governing clinical trials. Prior to the commencement of the trial, approval must be obtained from the Ethics Committee, and the trial may only be conducted after such approval has been granted. Any modifications to the trial protocol must be approved by the Ethics Committee prior to implementation.

Prior to the start of the trial, an informed consent form must be provided to each participant, and they must be instructed to read it carefully. The study physician is responsible for explaining the contents of the informed consent form in detail and addressing any questions the participant may have. The participant must be fully informed about the purpose of the trial, the treatment regimen, laboratory tests, potential risks, and their rights and benefits. Participants must also be informed that they may choose alternative treatment options and withdraw from the trial at any time without facing any adverse consequences. Each patient must voluntarily sign the informed consent form before entering the trial. The study physician must ensure that all informed consent forms are properly stored in the study records. The privacy of participants must be protected, and information related to their participation in the trial must not be disclosed without authorization. If necessary, the drug regulatory authorities, ethics committee, or sponsor may review the records of participants in the trial in accordance with applicable regulations.

8. Research Management

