3.2 Study Population Grouping

Participants will be randomly assigned into two groups: the intervention group (Group A) and the control group (Group B), with 100 participants in each group. Randomization will be conducted using SAS software version 9.4 or higher, employing a block randomization method to generate a reproducible randomization table. Randomization will be implemented via sealed envelopes, assigning eligible participants to either Group A or Group B in a 1:1 ratio.

After randomization, physicians will prescribe antidiabetic medications according to standard clinical practice. The use of sulfonylureas, meglitinides, insulin, or insulin analogs is prohibited in this study due to the risk of hypoglycemia.

During the first month of follow-up, GA levels will be measured in Group A. Based on the principle of "GA normalization," physicians will adjust the treatment regimen accordingly (details in section 3.3.4.2). Blood samples will also be collected during the second and third months of follow-up for GA measurement, but these results will not be used to adjust treatment; they are solely for statistical analysis.

In Group B, blood samples will be collected at the same time points (1st, 2nd, and 3rd months) for GA measurement, but these results will also not be used for treatment adjustments and will be used only for statistical analysis.

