3.1. Research groups

Subjects will be randomly assigned to two groups:

- Intervention Group (Group A)
- Control Group (Group B)

Each group will consist of 100 subjects. Randomization will be performed using block randomization generated by SAS version 9.4 or later, ensuring reproducibility. Randomization letters will be used to assign eligible subjects in a 1:1 ratio to either Group A or Group B.

All subjects will receive antidiabetic treatment according to standard clinical practice. The use of sulfonylureas, glinides, insulin, or insulin analogs is prohibited in this study.

At the first follow-up visit (Month 1), GA will be measured for subjects in the intervention group. Based on the GA normalization principle, the investigator will adjust the treatment regimen accordingly. At Month 2 and Month 3, blood samples will be collected, and GA will be measured after the follow-up period,

but these results will not be used to adjust treatment and will be used only for statistical analysis.

Subjects in the control group will also have blood samples collected at Month 1, Month 2, and Month 3, with GA measured after the follow-up period for statistical analysis only.

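### Protocol 6 pairs competitive enrolment with a 10 + 10 quota per centre; if the quota is enforced while arms are visible, the last allocations at each centre are known in advance.

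*Protocol*

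**What the plan says.** Protocol section 6 (case allocation among centres) opens with "This trial uses a competitive enrollment method". The same sentence goes on to say that "each center will recruit 10 subjects in the control group and 10 subjects in the intervention group", and it puts the trial as a whole at 100 per arm. Neither document gives the number of centres.

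Protocol 3.2 describes the randomisation as "employing a block randomization method to generate a reproducible randomization table". On how the list is applied, it says: "Randomization will be implemented via sealed envelopes, assigning eligible participants to either Group A or Group B in a 1:1 ratio". SAP 3.1 repeats block randomisation and 100 per group, does not mention a centre quota, and names a slightly different device: "Randomization letters will be used to assign eligible subjects in a 1:1 ratio to either Group A or Group B". Neither document states the block size, whether blocks vary, whether the list is stratified by centre, or who holds the envelopes.

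Neither document uses the term open-label. Protocol 3.3.4 nevertheless makes the arm visible: Group B does not attend Visit 3B, and for Group A "The GA results for Group A patients will be communicated to the study physician and the patients".

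**The concern.** Competitive enrolment leaves each centre's total free until the trial is full. A fixed 10 + 10 sets it at 20 and also fixes the split by arm. Read literally, a site cannot follow both.

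The split by arm matters more than the total. Staff who know each patient's arm can count. Once ten patients at a centre are in one arm, a binding quota sends everyone else there to the other arm. A sealed envelope cannot hide an allocation that has been worked out by counting.

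The protocol leaves room to act on that knowledge. Screening HbA1c (7.5% to below 10.5%) is available before randomisation and plausibly bears on the chance of reaching below 7%. Two exclusions rest on the investigator's judgement: 3.1.3.9 (need for a prohibited drug class) and 3.1.3.11 (unsuitable for observation). The primary test is an unadjusted chi-square or Fisher test (Protocol 5.5, SAP 7.4.1). The CMH sensitivity analysis adjusts for centre only, so it would not remove selection of patients within a centre.

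**Working it through.** **Inputs from the documents.** 10 per arm per centre and 100 per arm in total (Protocol 6); 1:1 blocks (Protocol 3.2); a planned difference of 30 points (Protocol 3.5). **Assumptions.** The quota is enforced, each centre's list is balanced over its 20 patients, and patients a site could choose between differ by D = 10 to 20 points in response chance. The documents give no source for D.

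**Step 1: the plan's own total.** 100 ÷ 10 = 10 centres. The total is reproduced only with exactly ten centres.

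**Step 2: the minimum.** With 10 + 10 fixed, the 20th allocation at a centre always follows from the first 19. That is 1/20 = 5%, or 10 of 200 over ten centres, whatever the block size.

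**Step 3: the average.** In a random balanced sequence with m patients per arm, the m patients of one arm fall on average equally into the m + 1 gaps around the other arm. The expected number after the last patient of the other arm is therefore m/(m + 1). Either arm may be the one that fills first, so the expected number of known allocations at the end is 2m/(m + 1). For one set of 20, m = 10: 20/11 = 1.82 of 20, or 9.1%. Over ten centres this is 18.2 of 200.

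If the 20 are made up of smaller whole blocks and the site does not know their size, only the end of the last block is revealed by the quota:

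| Block size (assumed) | Known at the end, 2m/(m + 1) | Share of 20 |
|---|---|---|
| 2 | 1.00 | 5.0% |
| 4 | 1.33 | 6.7% |
| 10 | 1.67 | 8.3% |
| 20 | 1.82 | 9.1% |

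**Step 4: possible bias.** Suppose a site acts only on certain allocations, placing the more favourable patient in A and the less favourable in B, or the reverse. With c the share of certain allocations, one arm's response rate shifts by +cD/2 and the other's by −cD/2. The bias is c × D.

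- c = 0.091: 0.091 × 10 = 0.9 points; 0.091 × 20 = 1.8 points.
- c = 0.05: 0.5 to 1.0 points.

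Against the planned 30 points, 0.9 to 1.8 points is 3% to 6%.

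**The case against.** The best defence is that section 6 introduces the figure as a plan for distributing cases. A planned distribution can sit beside competitive recruitment, and no text says that an arm closes at a centre when it reaches 10. This stands in part: if 10 + 10 is a target, the certainty created by the quota disappears. But the wording is that each centre will recruit these numbers, so the sentence still has to be reconciled.

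Three stronger readings are tempting, and the documents do not support them.

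- A reader might infer that the quota could be met only by chance or by departing from the list. That does not follow. If each centre receives whole blocks totalling 20 (size 2, 4, 10 or 20), the list itself yields 10 + 10. Silence on centre stratification does not show that it was absent.
- A reader might note that a coin toss gives exactly 10/10 at one centre only 17.6% of the time (C(20,10)/2^20). Protocol 3.2 specifies blocks, so that figure does not describe this trial.
- A reader might take fixed blocks of 4, with 33% of allocations certain and 71% guessable, and arrive at a bias of up to about 8 points. That needs block sizes that are fixed and known to sites, and sites that act on every guess. It would come from the blocks and would remain if the quota were deleted. The block size is not stated.

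The text may also be out of date. The protocol supplied is Version 2.0 (December 2021); SAP section 1 says it is based on Version 3.0 (March 2023), which was not supplied. Section 6 may have been revised.

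**Conclusion.** The point holds in a limited form. Section 6 contains two enrolment rules that agree only if one of them is a target. Its quota, if enforced, weakens concealment in a trial where staff can see the arm. That visibility is inferred from the visit procedures, though the inference is strong.

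Once enforcement is granted, the 5% minimum needs no assumption about block size. The 9.1% average needs one balanced set of 20 per centre. The 0.9 to 1.8 points also need the assumed 10 to 20 point difference between patients and sites that act on every certain allocation. The documents give no evidence that any site did so. Smaller fixed blocks known to sites would add predictability, by an amount that cannot be fixed from the documents.

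This is a small, avoidable weakness in a primary comparison that is unadjusted. It does not show that the result is biased.

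**What to change.** In Protocol 6, delete the per-arm quota and keep competitive enrolment, with at most a cap on each centre's total. A cap on the total says nothing about the next arm. State the number of centres.

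In Protocol 3.2, state that the list is stratified by centre, with block sizes that vary at random and are withheld from sites, and say who holds the envelopes. Use the same description in SAP 3.1.

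The cost is protocol wording and a regenerated list for patients not yet randomised. The downside is that arms may differ slightly in size within a centre, by at most half the block left unfinished there. The CMH sensitivity analysis would then match the randomisation; the primary test would still ignore centre.

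The SAP is dated October 2024 and the documents do not give enrolment status. If enrolment is complete, the list cannot be changed. The report should then say how it was built, whether it was stratified by centre, what block sizes were used and whether sites knew them, and whether any arm was closed at a centre. Whichever applies, check section 6 against Protocol Version 3.0.
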